Context: Craniosynostosis is a common craniofacial abnormality which can be associated with various clinical syndromes. Though it has been established that children with craniosynostosis score lower on certain developmental tests, the effect of craniosynostosis and cranioplasty surgery on the neural circuitry and brain development is less well known or understood.

Objectives: The purpose of this study is to describe the effect of cranial vault remodeling in children with craniosynostosis on white matter tracts with tractography and Diffusion tensor imaging (DTI), functional MRI, and neurodevelopmental tests, before and after surgery as compared to age-matched controls.

Study Design: This will be a prospective study of patients diagnosed with craniosynostosis and who are going to have open or endoscopic cranial vault remodeling (CVR).

Study Measures: The study will measure MRI sequences before and after surgery and at set time intervals to quantify the effect of white matter tract maturity. Parallel to this, neurodevelopmental tests will be administered at these same intervals.

Background and Rationale

Introduction

Craniosynostosis, the premature ossification and fusion of one or more cranial sutures, is a common craniofacial abnormality occurring in 1 of 2,000 live births.^{1 2} Craniosynostosis can lead to increased intra-cranial pressure in between 12-50% of those affected which may have delayed neuro developmental implications.

The crucial neurodevelopment occurs in the first years of life and is most rapidly progressing during the first year of life. Premature closure of the cranial sutures decrease the intracranial volume and space available for the rapidly developing brain. Cranial vault remodeling (CVR) is the current standard of care to mitigate any possible developmental delay secondary to craniosynostosis and also improve the head shape. CVR is a combined surgery between the neurosurgeon who takes off the cranial bone/bones, and the craniofacial surgeon who assists and reconstructs the cranium with absorbable plates and screws.

After surgery, although there is no doubt that there is an improvement in head shape, the craniofacial skeleton and the soft tissues, but there is less data, and virtually no functional imaging information available addressing the effect of CVR surgery on the growing brain.

Title: Neurodevelopmental Outcomes in Craniosynostosis Repair
PI: [name]
Site: Arkansas Children's Hospital
Funding: UAMS Intramural Grant

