Other groups have begun to look at DTI as a methodology to examine the changes in the brain in children with craniosynostosis, but in older children^{9 11}, this group found that, "Although these patients have a normal fiber organization, increased diffusivity parameters suggest abnormal microstructural tissue properties of the investigated white matter tracts." Thus far, only animal studies demonstrate the effect of the CVR in a rabbit model of craniosynostosis, which suggests enhanced white matter tracts following intra-cranial expansion^{12, (12)} As this is a pilot study, we will plan to recruit our own control subjects, age matched to our test subjects, but also plan to compare them with de-identified publicly, available datasets, i.e., the Baby Connectome project once they are made available.¹³ Our hypothesis is that CVR has a positive effect on white matter tract development and our proposed study seeks to perform the first human study of the relevant patient population.

Study Aims

Aim 1: We will *establish* pilot data to establish a normative curve of white-matter tract development in normal children under 4 years of age using (DTI). Fractional anisotropy (FA) (a main DTI parameter sensitive to white matter integrity) maps will be created to achieve a normative "white matter change curve" with from infancy to pre-school age.

Aim 2: Will *quantify* the change in white matter tract organization after cranial vault remodeling (CVR) surgery in patients with craniosynostosis by analyzing pre- and post-operative DTI data. This experimental cohort will also be examined in comparison to age-matched controls as compiled in Specific Aim #1, pooled with other centers and compared with published data sets of normal babies from the Baby Connectome Project. . The imaging will be repeated at three intervals after surgery leading up to approximately 4 years of age.

Aim 3: Will assess neurodevelopmental test results in craniosynostosis patients and seek to *correlate* these findings with white matter tract changes.

Title: Neurodevelopmental Outcomes in Craniosynostosis Repair
PI: [name]
Site: Arkansas Children's Hospital
Funding: UAMS Intramural Grant

Study Population

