This will be a prospective, longitudinal observational study. Prospective subjects will come from those patients seen as they present to the plastic and/or neurosurgery clinics and a diagnosis of craniosynostosis is suspected. Subsequently, if surgery is indicated, these patients will be approached and considered for inclusion the study. Of note, regardless of study participation it is our practice to follow children with CVR annually until the age of skeletal maturity, i.e., between 16-18 years of age. Annual visits may include but are not limited to the clinic exam, imaging, neurodevelopmental testing and or laboratory blood work, all of which are part of the standard of care for children with craniosynostosis.

We estimate that the duration of this study to be completed by December 31, 2030. We intend to include up to 500 subjects diagnosed with craniosynostosis and up to 60 normal control subjects in this study. The normal control subjects will undergo only a single MRI without sedation, using previously published calming techniques ¹³ and a single Bayley and/or Mullen Scales (age appropriate) administered just prior to the MRI. If the child is deemed within normal limits, they can proceed to the MRI imaging.. We plan to recruit normal, age-matched controls with an awarded UAMS Research Scholar Pilot grant. We will recruit control patients from our neurosurgery and plastic surgery clinics. These patients will be chosen amongst healthy children as stated in the inclusion /exclusion criteria. We expect these patients to be mostly patients who are referred to our clinic with abnormal head shapes due to position but does not have craniosynostosis or any related health problems.

Inclusion Criteria

- Up to 500 children, for all subjects, age of initial study entry: one test group between 3-6 months old (endoscopic assisted), and the other 6-24 months of age (open CVR)) once enrolled, children will be included until 4 years of age.
- Diagnosed with craniosynostosis, single or multiple suture
- Babies with craniosynostosis syndrome including but not limited to Pfeiffers, Aperts, Cruozons, Muenkes.

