component for test subjects who, for developmental or behavioral reasons, could not successfully complete an imaging study necessary for diagnosis and completion of the study. We will carefully detail the risks of performing the MRI under sedation as expanded in the risks section below. One Pre-operative MRI is clinically indicated to establish and confirm the diagnosis and the three post-operative MRI's will be done for research purposes.

Surgical Component (Plastic Surgery & Neurosurgery)

Once patients are identified and surgery is planned, the standard of care procedures fall into two categories based on age of presentation and clinician judgement and family preference all other things being equal. Both the endoscopic-assisted craniectomy and open CVR are standard of care procedures performed at every major craniofacial center. The ideal candidate for endoscopic-assisted craniectomies are infants with confirmed craniosynostosis (typically sagittal) who present at an age in which they can be operated on within 3-6 months of age. The ideal candidate for open CVR is any patient with confirmed craniosynostosis in which surgery can be performed after 6 months old. It has been our experience that these patients self-select into these groups solely by what age they present to our clinic. None of the surgery performed nor any aspect of the surgery is experimental.

Neurodevelopmental Assessment Component

Under direction of [name] and her teams routinely examine patients with craniosynostosis both pre-operatively and post-operatively as part of American Cleft palate craniofacial Association (ACPA) guidelines and standard of care. Thus, these examinations are part of the normal clinical exam and part of the medical record. The Bayley Scales of Infant and Toddler Development are used up to and including age 4 and the Mullen Scales of Early Learning are used from birth to 68 months.

Control Group Neurodevelopmental Assessment

Control subjects will be tested by ACH but if published MRI and developmental testing are readily available and sufficient for data analysis that will be used instead of enrolling control patients.

Schedule of Imaging and Neurodevelopmental Assessment

1. **PRE- OP** Within 30 days of the surgery date (all 3 components may occur on the same day or different days for family convenience):

Title: Neurodevelopmental Outcomes in Craniosynostosis Repair
PI: [name]
Site: Arkansas Children's Hospital
Funding: UAMS Intramural Grant

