- pre-anesthesia testing (45-minute duration) & pre-operative phlebotomy including, type and screen (2-4ml), complete blood count (CBC) (0.5ml), and possibly basic metabolic panel (0.5ml), and coagulation panel (2-4ml)
- initial neurodevelopmental testing (Bayley and Mullen Scales – 1 hour duration performed by [name]. [name])
- preoperative MRI functional sequences (60 minute duration) (research-related)

2. Surgery Day: Two cohorts:

- endoscopic-assisted group (age range at surgery between 3- and 6-months old) and
- Open cranial vault remodeling group (age range at surgery between 6- and 24-months old).

3. Six (6) to 6-months post-op:

- clinic visit,
- Neurodevelopmental testing (research-related)
- repeat MRI Imaging(60 minute duration) (research-related)

4. Twelve (12-) to 18-months post-op:

- clinic visit,
- Neurodevelopmental testing (may be repeated earlier at 9-15 months if clinically indicated) (research-related)
- Repeat MRI imaging(60 minute duration) (research-related)

5. Pre-school age (4 years old and younger):

- clinic visit
- Neurodevelopmental testing (research-related)
- repeat MRI Imaging(60 minute duration) (research-related)

Risks and Benefits

One potential risk to study participants is the potential for loss of confidentiality. Measures to protect the confidentiality of study participants will be implemented as described in the Data Handling and Recordkeeping section below. Another potential small risk is the additional anesthesia for the research related MRI's both in terms of the subjective experience of the test subjects themselves and risk of administering

Title: Neurodevelopmental Outcomes in Craniosynostosis Repair
PI: [name]
Site: Arkansas Children's Hospital
Funding: UAMS Intramural Grant

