A master key list of study subject identifiers including names, MRNs, and five-digit study IDNs will be maintained on a password protected computer. As this is a study at ACH, we will also be registering test and control subjects into the Clinical Trials Management System. The study subject identifiers will not be linked to the study data. All study subject identifiers in the master list will be destroyed after publication. De-identified study data will be backed up by maintaining a copy on the computer of the principal investigator [name] and co-investigator [name] MBBS, with the original on the ACH password-protected shared drive server. De-identifiable study data will be retained indefinitely.

Regarding the data from other sites, only de-identified, data will be pooled for analysis, ie quantitative data from the DTI analysis and neurodevelopmental results. Each outside site, will be responsible for de-identifying its own data set for pooling with ours. UAMS will be the repository for the data analysis, and the central database we will keep will ONLY contain the 5-digit IDN. Each institution will retain its key for the IDN and corresponding patient identifiers.

The data safety monitor(DSM) will be an appointed clinical team member, ([name], PA) who will NOT be responsible for recruiting patients into the study but rather have the role of communicating with the PI's mentioned above ([name] [name]) and study coordinator about unanticipated problems, deviations from protocols and/or modifications. If an AE or SAE occurs as defined in the section above to any subject in the study, the study coordinator will relay this information to the IRB in the appropriate time frame but also will notify the DSM to make note in routine reports to the IRB on study progress.

Data Analysis

Primary and Secondary Endpoints

- 1) Understand to a previously unreported level of detail the brain function in children with craniosynostosis using DTI-MRI sequences as compared with age-matched controls
- 2) Determine the effect of CVR on brain development in comparing pre and post-operation DTI-MRI sequences at several intervals post-operatively
- 3) Identify the relationship between the brain development changes as seen on DTI with cognitive testing results

Note that from this master group, multiple cohorts will be grouped for analysis, i.e., single suture and multiple suture craniosynostosis, syndromic craniosynostosis. We

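### Endpoint 2 asks for the effect of CVR, but because every patient is operated on, the planned comparisons cannot separate it from how the patient–normal gap would have moved without surgery

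*Combined protocol and SAP*

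**What the plan says.** The opening synopsis (Study Design) defines the cohort as "patients diagnosed with craniosynostosis and who are going to have open or endoscopic cranial vault remodeling (CVR"). Study Population confirms it: "Subsequently, if surgery is indicated, these patients will be approached and considered for inclusion the study". No unoperated or delayed-surgery craniosynostosis group is described.

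The claim to be tested is causal. Relevant Literature and Data states: "Our hypothesis is that CVR has a positive effect on white matter tract development". Endpoint 2, under Primary and Secondary Endpoints, reads: "Determine the effect of CVR on brain development in comparing pre and post-operation DTI-MRI sequences at several intervals post-operatively".

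Aim 2 provides two kinds of comparator. One is each patient's own pre-operative scan. The other is normal children: the study's controls ("This experimental cohort will also be examined in comparison to age-matched controls as compiled in Specific Aim #1"), who have one MRI each, and an external set ("compared with published data sets of normal babies from the Baby Connectome Project").

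Statistical Methods lists simple group tests, a repeated measures analysis of pre- and post-operative data, and comparisons of DTI parameters between patients and controls or between ages. Sedation is to be an analysis variable. Operated and not-yet-operated patients of the same age are never set against each other.

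The schedule places the pre-operative scan within 30 days of surgery. Surgery is at 3 to 6 months in the endoscopic group; the other is given as "Open cranial vault remodeling group (age range at surgery between 6- and 24-months old"). On how children reach a group, Surgical Component says that "these patients self-select into these groups solely by what age they present to our clinic", but the same paragraph also names clinician judgement and what the family prefers.

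**The concern.** Healthy controls, however well modelled by age, show how a normal brain matures. They do not show how the brain of a child with unoperated craniosynostosis would have matured over the same months. If the gap to normal narrows with age on its own, surgery is credited with it. If the gap widens on its own, a real benefit is hidden.

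The second case matters to the sponsor. The protocol's own rationale is that early fusion limits space for a fast-growing brain and that skull distortion progresses, so a stable unoperated gap is not the obvious default. At stake is whether endpoint 2 can support any statement about what surgery does, as opposed to what is seen after it.

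**Working it through.** The documents give no DTI effect size, SD or power calculation, so there is no figure to reproduce. Three checks follow.

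**1. What the planned change estimates.** Let D be a child's deviation from the normative curve in control SDs, U(a) the mean D of unoperated patients at age a, and τ the CVR effect. With the pre-operative scan at age a₀ and the post-operative scan at a₁:

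- pre-operative mean = U(a₀)
- post-operative mean = U(a₁) + τ
- change = τ + [U(a₁) − U(a₀)]

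Controls fix the zero line of D. The child's own pre-operative scan supplies U(a₀). Neither supplies U(a₁). With a linear drift of g SD per year and a scan 6 months after surgery, the change is τ + 0.5g. The values of τ and g below are assumed:

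| True effect τ | Drift g per year | Apparent change |
|---|---|---|
| 0.3 | 0 | 0.3 + 0 = 0.30 |
| 0 | +0.6 | 0 + 0.3 = 0.30 |
| 0.6 | −0.6 | 0.6 − 0.3 = 0.30 |
| 0.3 | −0.6 | 0.3 − 0.3 = 0 |

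A simulation agreed (400 replicates; assumed 40% endoscopic, between-child SD 0.7, scan error SD 0.5). Going from 50 to 500 patients cut the standard error of the change from about 0.10 to 0.03 and left the bias as it was.

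**2. Whether the schedule contains an unoperated reference.** Inclusion Criteria set entry at 3 to 6 months (endoscopic) and 6 to 24 months (open), and consent precedes study procedures. Pre-operative scans therefore cover about 3–24 months overall and 6–24 months in the open group. The first post-operative window is garbled, with six months printed at both ends; it is read here as 6 months.

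- Endoscopic, first scan: 3+6 to 6+6 = 9–12 months. Second scan: 3+12 to 6+18 = 15–24 months. Both lie inside 6–24. If the first window ran to 12 months after surgery, ages would be 9–18, still inside.
- Open, first scan: 12–30 months. It is covered when surgery is at 18 months or earlier. With age at surgery assumed uniform, that is (18−6)/(24−6) = 67%.
- Open, second scan: 18–42 months. It is covered when age at surgery is at most 24 minus the interval. With a mean interval of 15 months, that is (24−15−6)/18 = 17%.
- If open surgery ages were skewed young (triangular, peak at 6 months), the two open figures would be about 89% and 30%.
- Any scan after 24 months: 0%, because no child is unoperated by then.

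**3. What a same-age contrast would estimate.** Operated minus not-yet-operated at age a₁ = τ + S, where S is the difference in underlying severity between the two sets of children. If S = 0, the simulation recovered true effects of 0, 0.3 and 0.6, with standard errors of about 0.15, 0.10 and 0.05 at 50, 100 and 500 patients. If severity shifts by s SD per year of age at surgery, the reference children are those operated on 6 months later, so S = −0.5s. With τ = 0.3 and s = ±0.3, the estimate is 0.3 ∓ 0.15, that is 0.15 or 0.45.

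**The case against.** The study calls itself a pilot, observational and a beginning of exploration. Aim 2 itself speaks of quantifying change after surgery, which is descriptive and achievable. CVR is presented as standard of care, so the absence of an unoperated arm comes with the setting. The analysis section plans several cohort groupings and leaves comparison between ages open, so the same-age contrast is unspecified rather than excluded. The contrast also has its own untestable assumption: a modest severity gradient moves a true 0.3 to 0.15 or 0.45. Overlapping age ranges do not guarantee enough children at each age, and setting endoscopic post-operative scans against open pre-operative scans compares different case mixes.

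Most of this stands, and it limits the remedy. It does not remove the problem: endpoint 2 and the hypothesis are worded causally, and nothing in Aim 2 or Data Analysis restricts the claim. The only remark about attribution is in Risks and Benefits and concerns anaesthesia.

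Two stronger readings are tempting. A reader might infer that healthy children are the only comparator; Aim 2 also uses each patient's own pre-operative scan, although one unoperated point gives no slope. A reader might also infer that the same-age contrast is clean enough to carry every claim about CVR, since groups are said to form by age at presentation alone. The same paragraph gives other determinants, so the documents do not support that.

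**Conclusion.** The planned analyses do not identify endpoint 2. The change they estimate is the sum of the CVR effect and the unoperated drift, and neither age adjustment nor sample size separates the two. This follows from the design and needs no assumed number. The size of the error cannot be given from the documents; the 0.30 SD examples show only that quite different truths can look alike.

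Scans already scheduled allow a partial answer up to about 24 months of age. Coverage is complete by age range for the first two endoscopic post-operative scans, given the 6-month reading of the garbled window. It is partial for the open group: about 67% and 17% under uniform age at surgery. That answer is supportive only. It assumes that age at surgery is unrelated to severity within the strata compared, and it estimates surgery together with its anaesthesia. Beyond 24 months, including preschool scans after that age, the study can report a remaining gap to controls but not a surgical effect.

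**What to change.** 1. Word endpoint 2 as change after surgery relative to normal children. State that beyond 24 months of age, including at the preschool scan, only the remaining gap to controls is reported.
2. Add a supportive analysis comparing already-operated with not-yet-operated craniosynostosis children at the same age at scan, with all pre-operative scans as the unoperated reference (about 3–24 months overall, 6–24 months for the open group). Run it within suture type and syndromic status, and include the open cohort where ages overlap. Adjust for scanner (3T or 1.5T), site and sedation, and allow for the same child contributing scans on both sides.
3. Let any statement about a CVR effect rest on this analysis together with the pre–post change, with its limits stated: non-randomised, two accounts of how groups form, surgery not separable from its anaesthesia, and possibly few children at the older pre-operative ages.
4. Reconcile the two accounts of group selection in Surgical Component, and correct the first post-operative window in the schedule.

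The cost is in wording and analysis; no scan, visit or patient is added. The price is lower precision (standard error about 0.15 against 0.10 at 50 patients, under the simulation's assumptions), residual selection bias and a weaker preschool claim.

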- Approximately 60 age-matched **controls** (3 in each group) not diagnosed with craniosynostosis syndrome, stratified by age groups starting at 3 months, 5 months, 7 months, 9 month 11 months, 13 months, 15 months, 17 months, 19 months, then every 3 months, 22 months, 25 months, 28 months, 31 months, 34 months, 37 months, 40 months, 43 months, 46 months, 49 months.

Title: Neurodevelopmental Outcomes in Craniosynostosis Repair
PI: [name]
Site: Arkansas Children's Hospital
Funding: UAMS Intramural Grant

Exclusion Criteria

- Children not meeting the inclusion criteria
- Children with traumatic brain injury, brain cancer, or VP shunt that could affect development.
- Children who have already undergone CVR repair
- **Developmentally Normal children who cannot undergo or cannot be still for an awake or asleep non-sedated MRI**

Study Design and Procedures

This observational study intends to collect all available patient data, including but not limited to:

- Age
- Date of birth
- Sex
- Race
- Ethnicity
- Physical Examination
- Personal Medical History
- Family Medical History
- Presenting clinical status
- Craniosynostosis type
- Present surgical history and procedures
- Inpatient Progress notes
- Discharge summaries
- Clinic notes
- Other interventions
- All Laboratory Results
- All Imaging Results
- Neurodevelopmental Assessments

Title: Neurodevelopmental Outcomes in Craniosynostosis Repair
PI: [name]
Site: Arkansas Children's Hospital
Funding: UAMS Intramural Grant

Radiological Component

Standard-of-care at ACH and at other institutions is initial imaging to confirm the diagnosis of craniosynostosis and identify any other intra-cranial abnormalities. This initial imaging can be in the form of either a low-dose radiation computed-tomography (CT) of the head or a MRI. Post-operative imaging, either CT or MRI, is based on clinical indicators and not routinely performed on all patients. Once the patient is identified and consented for the study, we will implement an MRI-based protocol to look at both the bone and the brain, thus obviating the need for a CT scan, however, in some cases a CT scan may need to be obtained or have been obtained at an outside facility.

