Presurgical MRI will be done on a 3T MRI (Prisma Siemens MRI scanner) or 1.5T (Achiva, Phillips MRI scanner). The protocol for patients less than 18 months of age will be Sagittal T1, Axial inversion recovery (IR), T2, fluid-attenuated inversion recovery (FLAIR), susceptibility weighted image (SWI), diffusion weighted images (DWI), diffusion tensor imaging (DTI), resting state fMRI, and sagittal 3D GRE / FFE (on 1.5 T scanners) or 3D T1 VIBE (on 3T scanner).

The MRI protocol for patients over 18 months of age will be: Sagittal T1, coronal T2, Axial T2, fluid-attenuated inversion recovery (FLAIR), susceptibility weighted image (SWI), diffusion weighted images (DWI), diffusion tensor imaging (DTI), resting state fMRI, and sagittal 3D GRE / FFE (on 1.5 T scanners) or 3D T1 VIBE (on 3T scanner).

Post-processing of the acquired 3D GRE, FFE and T1VIBE sequences will be done on vitrea station. The acquired images will be reviewed by US board-certified pediatric neuroradiologists for single or multi suture craniosynostosis. Intracranial volume, ventricular size and sulcal crowding will be accessed. The DTI data will be analyzed on a password protected workstation by MRI physicist (Co-investigator, [name] and his research assistant, [name]) for evaluation of white matter microstructural integrity. Other imaging data from the same MRI sequences may also be exported to the workstation for additional quantitative analysis.

The expected time for MRI image acquisition is approximately 60 minutes for control subjects. If this process is prolonged greater than 2 hours due to control subject's lack of cooperation or discomfort then it will be aborted and will be re-scheduled. If the parents do not wish to proceed with a rescheduled time then the control subject will be removed from the study.

The MRI protocols will be identical for the control subjects and scheduled at the parent's convenience, but falling within one week on either side of their requested age. Because scheduling of the MRI may not allow this degree of control, control patients will be stratified by the age when they actually undergo the study not the age of recruitment. We will not plan to sedate the normal control subjects, however, sedation *may be a*

Title: Neurodevelopmental Outcomes in Craniosynostosis Repair
PI: [name]
Site: Arkansas Children's Hospital
Funding: UAMS Intramural Grant

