Title: Neurodevelopmental Outcomes in Craniosynostosis Repair
PI: [name]
Site: Arkansas Children's Hospital
Funding: UAMS Intramural Grant

plan to analyze data both for quality control and preliminary analysis every 6 months while the study is on-going.

Statistical Methods

For the complex analysis of large amounts of MRI data on the same patient and comparing with other patients, we plan to employ biostatistical support baseline and demographic characteristics will be summarized by standard descriptive summaries (e.g., means and standard deviations for continuous variables such as age and percentages for categorical variables such as gender).

Data will be presented as frequencies, medians with ranges, or \pm SD, as appropriate. Tests of group differences will include the paired t-test, χ^2 , and z-test, as appropriate. Repeated measures analysis will also be performed to on pre- and post-operative data for the same patient.

DTI parameters will be computed by standard software and will be compared between patients and controls or between different ages using standard statistical methods. Of note, for each MRI session, whether or not the participant was sedated will be a variable including in analysis.

Ethical Considerations

This study will be conducted in accordance with all applicable government regulations and Arkansas Children's Hospital research policies and procedures. This protocol and any amendments will be submitted and approved by the UAMS Institutional Review Board (IRB) to conduct the study.

The formal consent of each caregiver for their child, using the IRB-approved consent form, will be obtained before that subject is submitted to any study procedure. The caregivers of all subjects for this study will be provided a consent form describing this study and providing sufficient information in language suitable for subjects to make an informed decision about their participation in this study. The person obtaining consent will thoroughly explain each element of the document and outline the risks and benefits, alternate treatment(s), and requirements of the study.

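### Two MRI scanners are allowed, no rule assigns them, and scanner is absent from the planned analysis, so an unequal scanner mix would bias the DTI comparisons

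*Combined protocol and SAP*

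**What the plan says.** - **Pre-operative scans.** The Radiological Component section allows two machines that differ in vendor and field strength: "Presurgical MRI will be done on a 3T MRI (Prisma Siemens MRI scanner) or 1.5T (Achiva, Phillips MRI scanner". The sequence lists for children under and over 18 months both end with a choice that depends on the machine: "sagittal 3D GRE / FFE (on 1.5 T scanners) or 3D T1 VIBE (on 3T scanner". Both field strengths are therefore foreseen in both age protocols. DTI appears in each list without a scanner distinction.
- **Post-operative scans.** The Schedule of Imaging and Neurodevelopmental Assessment says only "repeat MRI Imaging(60 minute duration) (research-related" and names no machine. There are four scans per patient: "One Pre-operative MRI is clinically indicated to establish and confirm the diagnosis and the three post-operative MRI's will be done for research purposes".
- **Controls.** "The MRI protocols will be identical for the control subjects". This settles the sequences, not the machine.
- **Numbers.** Study Population: "We intend to include up to 500 subjects diagnosed with craniosynostosis and up to 60 normal control subjects in this study". The Inclusion Criteria plan three controls in each age group.
- **Analysis.** Statistical Methods compares DTI parameters between patients and controls and between ages, and adds a repeated-measures analysis of pre- and post-operative data. The one per-session variable it names is sedation: "whether or not the participant was sedated will be a variable including in analysis". It mentions no scanner term, and the documents describe no phantom calibration or harmonisation.
- **Pooling.** Data Handling and Dissemination of Data provide for pooling DTI values with other centres, again without a site or scanner term.

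**The concern.** The first two endpoints are contrasts of DTI values: patients against controls, and post-operative against pre-operative. If the two machines give systematically different DTI values for the same brain, any imbalance in their use appears in the contrast as an apparent effect of disease or surgery. Pairing within a child removes stable differences between children. It does not remove a change of machine between two visits.

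Imbalance is not certain, but it is plausible. The pre-operative scan is described as clinically indicated and the later ones as research. Control scans are unsedated and booked around the parents, while patients may be sedated. These are different booking routes, and nothing in the plan balances them over scanners. Aim 1, the normative curve, is exposed in the same way if scanner use drifts with age.

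Timing matters too. A scanner term added later separates the offset from the effect only if both machines are represented in the groups and time points compared. A child's scan at a given age cannot be repeated.

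**Working it through.** The plan gives no alpha, power, effect size, SD or scanner offset, so there is no stated figure to reproduce. What follows is the bias formula and an illustration.

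**Bias.** Let *d* be the additive scanner offset, in SD of the DTI measure, and let *p* and *q* be the shares of scans on a given scanner in the two sets compared. Then

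bias = *d* × (*p* − *q*).

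If *p* = *q*, the bias is 0 whatever the offset.

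**Patients against controls.** From the documents: 500 patients and 60 controls, both upper limits. Assumed: one age-adjusted value per child, a common within-group SD of 1 (scanner mix included), no true difference, a two-sided 5% test, and the offsets and share differences shown.

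SE = √(1/500 + 1/60) = √0.01867 = 0.1366

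Rejection rate = Φ(−1.96 + bias/SE) + Φ(−1.96 − bias/SE)

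| Offset (SD) | Share difference | Bias (SD) | Bias/SE | False-positive rate |
|---|---|---|---|---|
| any | 0 | 0 | 0 | 0.05 |
| 0.2 | 10 points | 0.02 | 0.15 | 0.052 |
| 0.5 | 30 points | 0.15 | 1.10 | 0.195 |
| 1.0 | 30 points | 0.30 | 2.20 | 0.593 |

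The result runs from negligible to severe, depending on two quantities the documents do not give.

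**Pre- against post-operative.** The same formula applies to the mean change: 0.5 SD × 0.30 = 0.15 SD is added to or taken from the estimated change, whatever the true change is. I give no rejection rate here. These are infants followed to about 4 years, and a test of zero change would be expected to reject from maturation alone.

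**How many pairs could switch.** If shares *p* and *q* of the pre- and post-operative scans are on one machine, at least |*p* − *q*| of the pairs are cross-scanner. If machines are chosen independently at each visit, the proportion is *p*(1 − *q*) + *q*(1 − *p*). For an assumed 70% against 30%, the minimum is 40% and the independent case gives 0.7 × 0.7 + 0.3 × 0.3 = 58%. For 60% against 40%, the figures are 20% and 0.6 × 0.6 + 0.4 × 0.4 = 52%. An imbalance large enough to matter therefore involves many pairs, and dropping them from the main estimate would be expensive.

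**Controls by age band.** The Inclusion Criteria list 19 starting ages with 3 controls each (57 in all). Three controls split 3/0 or 2/1 between two machines. If each scan falls on the 3T with independent probability *s*, a band lies wholly on one machine with probability *s*³ + (1 − *s*)³. That is 0.25 at *s* = 0.5 and 0.52 at *s* = 0.8, or about 5 and 10 of the 19 bands. Single bands thus carry little information on the offset. A curve fitted over all ages can estimate it, provided both machines are used across the age range.

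**After the change.** With one scanner per comparison, or with an additive offset correctly adjusted for and both machines represented in the sets compared, the bias is 0 and the false-positive rate returns to 0.05.

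**The case against.** The case on the other side has several sound parts.

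- The two-scanner sentence concerns presurgical MRI only. That a child may be scanned on the other machine after surgery is inferred from the schedule's silence. The over-18-month list, with both field strengths, makes the inference reasonable, but no sentence says so. This stands as a limit on wording.
- A reader might infer from the scanner-specific 3D sequences that identical control protocols are impossible. The text does not support that. The natural meaning is that controls follow the same protocol as patients. The sequence that differs is processed separately from the DTI, which is listed alike for both machines.
- A reader might also infer that three controls per band make the normative comparison unworkable. That would follow only if each band were analysed alone, and Aim 1 describes a curve across ages.
- The study calls itself a pilot, makes no power claim and plans biostatistical support. The sedation remark need not be a complete list of covariates, so a scanner term could be added. That is true, but a later term cannot repair scans in which machine and group, or machine and visit, coincide.
- No passage says the mix will differ, and every offset and share used above is assumed. This stands, and it limits the conclusion to a risk.
- Naming one local scanner leaves the other centres and the Baby Connectome Project data on their own machines. This also stands, and it is a reason to record site as well.

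**Conclusion.** The gap is real: two machines are permitted, nothing assigns or balances them, and scanner is not among the variables named for analysis. Followed as written, the plan can let a scanner offset enter the patient-control and pre-post DTI contrasts, with bias equal to the offset times the difference in scanner share.

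Its size cannot be derived from the documents. Under the stated assumptions the patient-control false-positive rate runs from 0.052 to 0.593, and it stays at 0.05 when the mix is equal. The documents do not support the stronger conclusion that the results will be biased, or that a particular error rate applies to the effect of surgery. No bias has been shown for the third endpoint, the relation between DTI and test results.

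This should be fixed. It is more than missing detail because the assignment of scanners has to be settled before the scans are made.

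**What to change.** **Radiological Component.** Name one scanner for all research DTI (pre-operative, post-operative and control) where feasible. Where it is not, keep each child on the scanner used at baseline, and spread controls over both scanners across the whole age range, so that scanner is tied neither to age nor to group. Placing each band's controls on whichever machine most patients of that age used would be unwise. It could tie scanner to age and leave the other patients without a same-scanner control.

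**Statistical Methods.** Record the scanner for every session, and the site for pooled data. Include them in every DTI model. For the second endpoint, keep all pairs in the main, scanner-adjusted estimate and report same-scanner pairs alone as a sensitivity analysis.

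**Cost.** Less freedom in scheduling, one extra model term (and a site term for pooled data), and slightly wider intervals.
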